Clinical Study Protocol

Drug Substance: Testosterone hormones
 Study Code: Pub-01 version 4
 EudraCT No 2012-002337-11
 Date: 30 January 2013

A multicenter and randomised clinical study on pubertal replacement therapy in boys - Treatment of boys with absent or delayed puberty with rhFSH and two different formulations of testosterone in low dose: Testoviron Depot® and Nebido®

Principal Investigator: [name], MD, PhD, Associate Prof & Senior Consultant of Pediatrics
 Sahlgrenska Academy-Gothenburg University Institute
 Clinical Science Department of Pediatric Growth research center
 Queen Silvia Hospital/SU/Ö [contact]
 [contact]
 [contact]

Co-investigator: [name] [name], PhD-student
 Senior Consultant of Pediatrics
 Pediatric Clinic
 NÄL, NU-sjukvården
 [contact] [contact]
 [contact]

Co-investigator: [name], MD, PhD,
 Senior Consultant of Pediatrics Pediatric Clinic
 Pediatric Clinic
 NÄL, NU-sjukvården
 [contact] [contact]
 [contact]

Monitor: Gothia Forum/CTC
 Sahlgrenska University Hospital /Sahlgrenska
 [name]
 [name]

Sponsor: Västra Götalandsregionen
 Sahlgrenska University Hospital /Östra
 [name]

The following Amendment(s) have been made to this protocol since the date of preparation:

Amendment No.	Date:
_____	_____
_____	_____

PROTOCOL SYNOPSIS

A multicenter and randomised clinical study on pubertal replacement therapy in boys - Treatment of boys with absent or delayed puberty with rhFSH and two different formulations of testosterone in low dose: Testoviron Depot® and Nebido®

EUdraCT number: 2012-002337-11

Principal Investigator

[name], MD. PhD, Associate Prof & Senior Consultant of Pediatrics
Sahlgrenska Academy-Gothenburg University
Institute clinical science
Department of Pediatrics
Growth research center
Queen Silvia Hospital SU
[contact]-
Fax [name]
[contact]

Study period

Estimated date of first subject enrolled: March 2013

Estimated date of last subject completed: December 2015 (group II) and December 2022 (group I)

Objectives

The primary objective of this study is to evaluate the effect of Testoviron Depot® and Nebido® on pubertal development in young males with delayed puberty and the effect of Testoviron Depot® and Nebido® in combination with Puregon in young males with absent of puberty.

Secondary objectives are serum testosterone levels during treatment with Testoviron Depot® and Nebido®, signs of masculinization and health-related quality of life (KIDSCREEN, JTJÄ).

Endpoints and variables

The primary endpoint in group I (boys with absent puberty) will be increase in blood LH after GnRH test. Testis size ≥ 8 mL will be the primary endpoint for group II (boys with delayed puberty).

Secondary endpoints are increase in testis size from baseline to 1 year (group I), serum testosterone levels during treatment with Testoviron Depot® and Nebido®, signs of masculinization from baseline to 3, 6 and 12 months, body growth, hair growth measured as tanner stage and inspection of axillaries hair, deepening of voice, gender identity and health-related quality of life.

TABLE OF CONTENTS	PAGE
PROTOCOL SYNOPSIS	2
TABLE OF CONTENTS	4
LIST OF ABBREVIATIONS AND DEFINITION OF TERMS.....	7
1. INTRODUCTION	9
1.1 Background	9
1.2 Rationale for conducting this study	10
1.3 Research hypothesis.....	11
1.4 Benefit/risk and ethical assessment.....	11
1.5 Ethical assessment	11
2. STUDY OBJECTIVES AND ENDPOINTS.....	12
2.1 Primary objective	12
2.1.1 Primary endpoint(s)	12
2.2 Secondary objective(s).....	12
2.3 Exploratory variables	12
3. STUDY DESIGN AND PROCEDURES	12
3.1 Overall study design and flow chart	12
3.1.1 Stopping criteria.....	15
3.1.1.1 Stopping criteria for dose continuation.....	15
3.2 Rationale for study design, doses and control groups.....	15
4. SUBJECT POPULATION.....	16
4.1 Inclusion criteria Group I (absent puberty).....	16
4.2 Inclusion criteria Group II (delayed puberty)	17
4.3 Exclusion criteria	17
4.4 Subject enrolment and randomization	18
4.5 Restrictions during the study	18
4.6 Withdrawal of subjects and study stop	18
4.6.1 Premature termination of the study.....	18
5. TREATMENTS	19
5.1.1 Doses and treatment regimens	19
5.1.2 Labelling	20
5.1.3 Storage	20
5.2 Concomitant medication and post-study treatment(s)	20

5.3	Treatment compliance.....	20
5.3.1	Accountability.....	21
6.	STUDY MEASUREMENTS AND VARIABLES	21
6.1	Screening and demography.....	21
6.1.1	Methods of assessments.....	21
6.1.2	Post-study.....	21
6.2	Bone age.....	22
6.3	LHRH-test.....	22
6.4	Pubertal stage.....	22
6.5	Signs of masculinization	22
6.6	Blood sampling.....	22
6.6.1	Study-specific blood samples	22
6.6.1.1	Haemoglobin (Hb)	23
6.6.1.2	LH and FSH	23
6.6.1.3	DHEAS	23
6.6.1.4	Testosterone and Estrogen.....	23
6.6.1.5	SHBG, AMH, InhibinB	23
6.6.1.6	Mass spectrometric analysis of steroids.....	23
6.6.2	Questionnaires.....	23
6.6.2.1	Standardize procedures for administration of questionnaires.....	23
6.6.2.2	KIDSCREEN	24
6.6.2.3	Jag Tycker Jag Är	24

1. INTRODUCTION

1.1 Background

Development and maturation of the reproductive system begins in fetal life and is an active process throughout the first postnatal months. During late pregnancy and the first months after birth the testosterone levels are high due to high activity in the hypothalamic (GnRH)/ pituitary/ gonadotropin (LH/ FSH)/ testis (testosterone) axis. After 3-6 months the activity decreases and remains low until start of puberty when the gonadotropic activity increases again. Male puberty begins when hypothalamic GnRH impulses start to stimulate the pituitary for release of gonadotropins (LH and FSH) during the night. This process normally starts at the age of 10-14 years.

The increased secretion of gonadotropins results in testicular enlargement from 1-2 mL to 3 mL and is the first physical manifestation of puberty. FSH stimulates the spermatogenesis by trophic effect on Sertoli cells and LH the Leydig cells to produce testosterone in the testis. The testis size of 3 ml represents transient phase from pre-puberty to puberty (1) and taking all the information on pattern and levels of testosterone together, the 3 mL testis can be seen to belong more to the pubertal stage than to the prepubertal stage. Testicular size continues to increase throughout puberty, reaching maximal adult size about 6 years after the onset of puberty. The volume of 4 mL or more is considered as the clinical landmark of puberty. Thus, delayed puberty is defined as no evidence of an increase in testicular volume (greater than or equal to 4 mL) by 15 years of age. The consequence of increased secretion of gonadotropins and testis enlargement is testosterone production which in turn leads to development of secondary male sexual characteristics. Testosterone plays an important role in the modulation of the male somatotrophic axis in adulthood, as it appears to be the case in puberty, and that this effect is partly dependent on the aromatization of testosterone to estradiol. Thus, the testosterone is the driver of the growth spurt and involved in the masculinization process. Gonadotropins reach the highest level during late night and early morning as a consequence also the testosterone levels are elevated early in the morning. Indeed, testosterone in early morning above 0.7 nM seems to predict progression of puberty with start of the pubertal growth spurt within 12-18 months. Early morning plasma testosterone is an accurate predictor of imminent pubertal development in pre-pubertal young males (2).

Factors that determine the timing of pubertal onset remain poorly understood and the subject of intense investigation but general health, nutrition and genetic factors all are known to contribute.

Approximately 2.5% of healthy adolescents are identified as having pubertal delay. Most are boys. Diseases that can delay the puberty of start are e.g. hypothyroidism, celiac disease, asthma and psychiatric disorders. Boys with late start of puberty or slow progression of puberty are rather common (3) and they may suffer both mentally and socially from this condition. In Sweden boys with delayed puberty are if they wish routinely treated with low dose Testoviron Depot® from the age of 14 unless no pathological disease is the cause the puberty delay.

1.2 Rationale for conducting this study

Boys with delayed or absent puberty have by tradition been treated with intra muscular injections of testosterone (Testoviron Depot®; Testosterone Enanthate) in low doses once a month. Although extensive clinical experience this therapy has not been evaluated in clinical trials, yet it has become the standard of care (SoC). Furthermore, Testoviron Depot® was unregistered 2006 and is now available only on licence in Sweden. During the last 6 to 8 years new testosterone replacement therapy has reached the market e.g. muscular injections of long acting testosterone (Nebido®), gels (Testogel®, Tostrex®, Testim®) and transdermal plasters Intrinsa®. These new treatments are labeled for adult men and women but not in children and adolescents. However, these products are being used off label today for the treatment of delayed or absent puberty in young males. The hormones have the possibility to be administrated in low doses by manipulation of the adult formulation, gel doses, transdermal patches or long acting intra muscular injections and thereby have the possibility to be used for treatment of delay of puberty in male adolescents. Intrinsa®, was however recently (May 2012) taken away at the European market.

A comparison between these products is important to make before Testoviron Depot® completely disappears from the market (not even available on license) which has been the SoC, based on clinical experience and not clinical trials.

In the present study, the treatment with Testoviron Depot® will be evaluated which would be an advantage since thorough clinical trials has never been performed. The treatment with Testoviron Depot® will be compared to low doses of solutions for intra muscular injections with Nebido®. Treatment with Nebido has the advantage to gels, both regarding the compliance of the treatment and it is easier to obtain the correct amount of the product for administration. With intra muscular injections of testosterone we have full control of how much testosterone is given. Furthermore we have limited clinical experience on what 200-250mg Nebido can result in testosterone levels seen in early and mid puberty for 3 months. The body's natural testosterone has a rapid turnover rate which requires a continuous production to maintain steady levels in the blood. This means that also substitution therapy must meet the requirement of even and "high" levels to have an optimal therapeutic effect. Thus, only formulations having different depot functions have been considered when choosing treatment in the present study.

The reason for having Puregon (rhFSH) as co-treatment in boys with absence of puberty is to mimic spontaneous puberty and optimize conditions for puberty to get started. In spontaneous puberty both FSH and LH increases, and in the present study FSH is substituted by Puregon and LH by its effect on Leydig cells as testosterone. Furthermore, the levels seen with low dose Nebido is more physiological since the testosterone levels are even and possibility to obtain similar to levels seen in spontaneous early or mid puberty compared to Testoviron which results in high testosterone similar or higher seen in adult males levels first 2-3 days after injection and thereafter decline to low levels last week before next injection. We will evaluate a new and more physiological combination therapy by combining FSH with Nebido and compare with the traditional Testoviron treatment in boys with absence of puberty. For boys with slow pace of puberty we will evaluate to principal forms of testosterone treatment for accelerating the pubertal development: Testoviron with high testosterone similar or higher seen in

adult males levels first 2-3 days after injection and thereafter decline to low levels last week before next injection to Nebido treatment were the testosterone levels are even and increased from early to mid puberty levels.

The study population will be selected among young male adolescents seeking care for delayed puberty involving worries about their height, physical appearance or concerns about the development of genitals and the emotional distress associated to the puberty development.

Long-term safety, more than 1 year, has not been evaluated in double blind placebo controlled studies. The present study will last for maximum one year. Moreover, only medically healthy young male subjects will be included in the study.

1.3 Research hypothesis

Does administration of testosterone with monthly rhythm induce puberty better than testosterone administered in more constant levels?

1.4 Benefit/risk and ethical assessment

Testoviron Depot® and Nebido® are anabolic steroids with high anabolic and androgenic effects. It is a long acting injectable testosterone that are used not only for medical purposes but also amongst athletes abuse since it increase strength, weight and muscle mass. Since Testoviron Depot® treatment is not evaluated there is no treatment benefit for boys in conventional group compared to the boys in the groups with new treatments.

Testosterone and estradiol will be monitored careful as too low levels will result in lack of effect and too high levels in adverse events e.g. aggressiveness, acne, Hb increase and potentially also impair long term growth due to early closure of growth zones. As testosterone and estradiol will be monitored careful during the study doses will be adjusted to give testosterone levels seen in early/mid puberty

1.5 Ethical assessment

The study will be conducted in compliance with ICH Good Clinical Practice and applicable regulatory requirements and in accordance with the ethical principles in the Declaration of Helsinki. For detailed information regarding ethics and regulatory review, informed consent, data protection and audits and inspections see **Appendix C** (Ethics).

Approval has been obtained from the ethic committee (IRB/IEC) in Göteborg (Dnr 506-12). Regulatory authorities will receive the clinical trial application (CTA) and required documents.

The investigator will ensure that the subject and parent/guardian are given full and adequate oral and written information about the nature, purpose, possible risk and benefit of the study and ensure that the subjects are notified that they are free to discontinue from the study at any time. Signed and dated informed consent should be obtained before conducting any study specific procedures and stored in the Study Master File. A copy of the signed Informed Consent Form is kept by the subject.

2. STUDY OBJECTIVES AND ENDPOINTS

2.1 Primary objective

The primary objective of this study is to evaluate the effect of Testoviron Depot® and Nebido® on pubertal development in young males with delayed puberty and the effect of Testoviron Depot® and Nebido® in combination with Puregon in young males with absent of puberty.

2.1.1 Primary endpoint(s)

The primary endpoint in group I (boys with absent puberty) will be increase in blood LH after GnRH test. Testis size ≥ 8 mL will be the primary endpoint for group II (boys with delayed puberty).

2.2 Secondary objective(s)

- Testis size (mL) in group I from baseline to 1 year (group I)
- Serum testosterone levels during treatment with Testoviron Depot® and Nebido®.
- Signs of masculinization from baseline to 3, 6 and 12 months (Body growth, hair growth measured as tanner stage and inspection of axillaries hair, deepening of voice, gender identity)
- Health-related Quality of life (KIDSCREEN, JTJÄ)

2.3 Exploratory variables

- LH and FSH
- Estradiol
- DHEAS
- SHBG, AMH, Inhibin B
- Mass spectrometric steroid profile of steroids

3. STUDY DESIGN AND PROCEDURES

3.1 Overall study design and flow chart

This is a prospective, randomized, controlled, open clinical study with parallel-group design. A total of 70 young males with delayed or absent puberty will be randomized to receive hormone replacement during 6 or 12 months. The study includes 9 or 10 visits at the clinic during a total period of 12 months.

To not expose boys for a new treatment (Nebido and Puregon in group I and Nebido in group II) that is inferior to Stand of Care Testoviron, a fertility test will be performed after 10 evaluable patients in each arm in the groups.

The subjects will be divided to two groups depending on whether they have I) absences of puberty (n=30) or II) delayed/slow progress of puberty (n=40):

I) Boys with absence of puberty (testis 1-3 mL and morning testosterone less than 0.5nM) will be randomized to two alternative pubertal replacement therapies; 1) low dose of Testoviron Depot® (SoC) 50 mg i.m. injection once a month or 2) rhFSH (Puregon®) and low dose Nebido® (one injection of 200 mg every 3 months). Those randomized to receiving rhFSH (Puregon®) and low dose Nebido® will start both treatments concomitant. The rhFSH (Puregon®) dose will be adjusted to reach serum FSH levels of 3-5IU/ml (see appendix D). This is expected to happen within one month (first check after one week after start of treatment with Puregon) and if not reach within one month of start of Puregon treatment the patient will be withdrawn from the study. Boys who have been randomized to Puregon/Nebido but at inclusion have serum levels of FSH above 3 will not be treated with Puregon, but if the patient during the study on 2 concomitant visits have serum FSH below 3IU/L he will be treated with Puregon to achieve serum FSH levels 3-5 IU/L during the rest of the study (see appendix D). The treatment will continue for 12 months. The effect will be evaluated after 6 and 12 months respectively on the development of masculinization and on spontaneous start of puberty. If the spontaneous puberty has started, the pubertal hormone replacement treatment will be stopped. The Nebido treatment will be dose adjusted in patients after the 1st injection if the testosterone profile shows to high or low levels; the goal is to have similar levels during 2 months as in early puberty (1-3 nM). For individual Nebido® adjustments in group I see appendix D.

II) Boys with delayed/slow progress of puberty (testis 4-6 mL and morning testosterone less than 4 nM) will be randomized to receive either 1) Testoviron Depot® (SoC) 75 mg i.m. injection once a month (SoC) or 2) Nebido® one injection of 250 mg at start and after 3 month. The treatment will continue for 6 months, dose adjustments will be possible after the first 4 patients on Nebido® (250 mg) for the rest of the study. The aim for the Nebido® treatment is to have morning testosterone levels in the lower range of mid puberty (4-9 nmol/L). An interim analysis has to be done after the first 5 patients and thereafter keep or adjust the dose (see appendix D for adjustment of the Nebido® dose for group II). The treatment will be evaluated after 6 month on development of masculinization and on spontaneous start of puberty after 12 months.

Figure 1 and Table 1 show the study overview and activities.

Figure 1a Study design Group I (absence of puberty)

[figure not shown]

Figure 1b Study design Group II (delayed puberty)

[figure not shown]

Table 1 Study activities

	Visit 1	Visit 2	Visit 3	Visit 4	Visit 5	Visit 6	Visit 7	Visit 8	Visit 9*	Visit 10
	Pre-	0	2 days	7 days	1 month	2 months	3 months	6 months	9* months	12 months
Informed consent	X									
Demography	X									
Medical history	X									
Nicotine use	X									
Weight, height	X						X	X	X	X
Pulse, blood pressure	X									
Physical exam	X									
Bone-age	X									
LHRH test	X									X*
Pubertal stage	X						X	X	X	X
HQOL	X							X		X
Hb, liver enzymes	X						X	X		X
LH, FSH	X	X		X*	X		X	X	X	X
DHEAS,		X						X		X
Incl/excl criteria		X								
Study drug		X								
Testosterone, estradiol		X	X	X	X	X	X	X		X

SHBG, AMH, InhibinB		X			X			X		X
Signs of masculinization								X		X
Plasma for masspektometri of steroids	X							X		X
Adverse events	X	X	X	X	X	X	X	X	X	X
Serious Adverse event recording	X	---	---	---	---	---	---	---	---	---

*Visit 9: Group I only

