4.1 Inclusion criteria Group I (absent puberty)

For inclusion in the study subjects must fulfil the following criteria.

1. Signed informed consent

2. Healthy young male subjects 14-16 years old
3. Morning serum testosterone value by inclusion (07.30-09.00) and start (08.00-10.00) that is less 0.5 nmol/L
4. Pre-pubertal LHRH test
5. Testicular volume 1-3ml bilaterally
6. Bone age 11 years or older
7. Otherwise clinically normal physical findings and laboratory values as judged by the investigator

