4.4 Subject enrolment and randomization

The investigator will obtain signed informed consent from the potential subject as well as both parent(s)/guardian(s) before any study specific procedures are performed. The investigator will thereafter determine subject eligibility according to study criteria and finally assign eligible subject unique *randomization code* (i.e. subject number).

Randomization codes will be assigned strictly sequentially as subjects are eligible for randomization. If a subject discontinues participation in the study, his subject number cannot be re-used. New subject gets a new number in consecutive order.

A randomisation schedule, containing randomisation code and treatment, will be provided by one of the study leaders.

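### Group I admits 3 mL testes, which the plan's own background calls nearer puberty, yet no stratum or adjustment for baseline testis volume is stated for a comparison of 15 against 15

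*SAP*

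**What the plan says.** Section 3.1 defines Group I by testis volume and morning testosterone: "Boys with absence of puberty (testis 1-3 mL and morning testosterone less than 0.5nM) will be randomized". Section 4.1 repeats the volume limit, "Testicular volume 1-3ml bilaterally", and sets the age range, "Healthy young male subjects 14-16 years old". It adds two hormonal conditions: "Morning serum testosterone value by inclusion (07.30-09.00) and start (08.00-10.00) that is less 0.5 nmol/L" and "Pre-pubertal LHRH test". Section 4.3 excludes boys in a growth spurt.

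Section 1.1 describes 3 mL as a transition and concludes that "the 3 mL testis can be seen to belong more to the pubertal stage than to the prepubertal stage". It puts the clinical landmark of puberty at 4 mL, and it ties the definition of delay to not having reached that volume ("greater than or equal to 4 mL) by 15 years of age").

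On allocation, section 4.4 says: "Randomization codes will be assigned strictly sequentially as subjects are eligible for randomization". A study leader supplies the schedule. The only division by pubertal status, in section 4 and Table 2, is between Groups I and II. Section 8 makes the Group I primary endpoint a yes/no pubertal LH response at 12 months and analyses it with Fisher's exact test. No stratum or covariate is named.

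**The concern.** The plan's background gives a reason to expect that boys at 3 mL are closer to onset than boys at 1-2 mL. The endpoint is whether the pituitary responds at a pubertal level a year later, so baseline volume probably predicts it in either arm. Group I has 15 boys per arm. If chance puts several more 3 mL boys in one arm, the crude difference will carry part of that imbalance, and nothing stated in the design or the analysis would remove it. A reader could take it for a treatment effect, or for the lack of one.

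The entry limits also do not sit easily with section 1.1. A 14-year-old with 3 mL testes enters as having absent puberty, while the background describes that volume as transitional and dates delay from age 15.

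**Working it through.** **The plan's own figure.** The plan gives no figure on this point. Its one worked calculation, in Appendix E, is for 20 per arm and reproduces. With 16/20 against 16/20 the standard error is √(0.008 + 0.008) = 0.1265, and the lower limit is 0 − 1.96 × 0.1265 = −0.248, inside −0.25. With 15/20 the lower limit is −0.05 − 1.96 × 0.1318 = −0.308, outside it. Hence 16 successes are needed. The present point does not rest on this.

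**Do the other entry criteria make volume irrelevant?**
- The testosterone ceiling of 0.5 nmol/L lies below the 0.7 nM that section 1.1 gives as a predictor of progression, with the growth spurt starting within 12-18 months. Section 1.1 does not say that a lower value rules out a pubertal LH response by month 12.
- The LHRH criterion in section 4.1 has no numerical cut-off.
- Section 3.1 evaluates spontaneous start of puberty in Group I at 6 and 12 months, so the plan expects that some of these boys may start.

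The screen therefore narrows the spread of risk. It does not show that 1 mL and 3 mL boys share one prognosis.

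**Chance imbalance.** Inputs: 30 boys, 15 per arm (Table 2). K, the number of boys with a 3 mL testis, is not given and is varied. For a random 15:15 split, the number x of such boys in one arm follows

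P(x) = C(K, x) × C(30 − K, 15 − x) / C(30, 15), with C(30, 15) = 155,117,520.

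The arms differ by |2x − K| boys.

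- K = 15: a difference below 3 needs x = 7 or 8, which is 2 × 41,409,225 = 82,818,450 allocations, or 53.4%. The rest is 46.6%.
- K = 10: a difference below 3 needs x = 4, 5 or 6, which is 35,271,600 + 46,558,512 + 35,271,600 = 117,101,712, or 75.5%. The rest is 24.5%.

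| K of 30 | differ by ≥ 3 | differ by ≥ 5 |
|---|---|---|
| 6 | 16.9% | 1.7% |
| 8 | 21.5% | 3.5% |
| 10 | 24.5% | 5.0% |
| 12 | 26.4% | 6.0% |
| 14 or 16 | 27.2% | 6.6% |
| 15 | 46.6% | 14.3% |

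The jump at 15 comes from parity. An even K allows only even differences, so three or more means four or more. An odd K allows three. By the same formula, odd counts from 7 to 13 give 39-46%. Letting K vary around an assumed share averages over both cases: the chance of three or more is 12%, 25%, 32% and 36% for shares of 10%, 20%, 30% and 50%.

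**What an imbalance is worth.** One boy is 1/15 = 6.7 points of an arm's success rate. If 3 mL boys succeed 20-40 points more often (an assumption; the plan has no data on it), three extra boys shift the expected difference by 3/15 × 20 to 40 = 4 to 8 points, and five by 5/15 × 20 to 40 = 7 to 13 points.

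**The case against.** The strongest reply is that Group I is defined by more than volume. A boy at 3 mL with testosterone below 0.5 nmol/L on two mornings, a prepubertal LHRH test and no growth spurt is hormonally prepubertal by the plan's own criteria. He is also below its 4 mL landmark. The remark in section 1.1 about 3 mL draws on testosterone pattern and levels, which section 4.1 screens. Age 14 has a basis too: section 1.1 says boys in Sweden are routinely treated from that age, and section 3.2 says the entry criteria resemble clinical routine. This stands. It defeats any claim that Group I is wrongly constituted, but it leaves the wording unreconciled.

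It is also fair that randomisation keeps the comparison unbiased without a stratum, that the study calls itself hypothesis-generating, and that the schedule is not shown and might contain strata that section 4.4 does not mention. These points limit the weight of the concern. They do not change the fact that the stated analysis ignores a cheap and plausible predictor in a very small comparison.

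A reader might go further and infer that boys who would start puberty anyway dilute a real deficit and so make non-inferiority too easy to show, and that stratifying would cure this. The documents do not support that inference. They give no share of such boys, and they do not say that a 14-year-old who passes the hormonal screen is nearer onset than a 16-year-old who does. A pooled stratified estimate averages over the strata, so it corrects chance imbalance and leaves any dilution in place.

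**Conclusion.** The point holds as a modest gap in design and analysis. Section 1.1 gives reason to treat baseline testis volume as prognostic, and the stated plan neither balances it nor adjusts for it. At 15 per arm, a difference of three or more 3 mL boys has a chance of about 17-27% for even counts of 6 to 16, and 47% at exactly 15. The size of the consequence is uncertain. It rests on two unknowns: how many boys have 3 mL testes, and how much better they do after passing the hormonal screen.

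The text does not justify calling the Group I result biased, or saying that these boys do not belong in the group. The tension between section 1.1 and sections 3.1 and 4.1 over 3 mL and age 15 is one of wording, to be reconciled or explained.

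**What to change.** 1. Stratify the Group I randomisation list by visit 1 testis volume: any testis of 3 mL versus both 1-2 mL. State this in section 4.4.
2. In section 8, prespecify a Group I risk difference stratified by the same factor, for example Mantel-Haenszel with a 95% confidence interval, reported alongside the Fisher test. If the list is already in use, this step alone still deals with chance imbalance on volume.
3. Label any results by volume or age subset as descriptive only.
4. Reconcile section 1.1 (3 mL, age 15) with sections 3.1 and 4.1, or state why they differ.

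The cost is two short blocked lists instead of one, and one extra estimate from data already collected at visit 1. The downside is that the arm sizes may end one or two boys apart.
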